3. an increased dose of corticosteroid before study week 8 and did not return to $<25\%$ above the baseline dose by week 12.

Endpoints:

1. **Primary Endpoint:**
 - a. Response rate at 40 weeks defined as percentage of patients meeting definition of improvement (DOI) in IIM patients treated with belimumab and standard therapy compared to the percentage of patients meeting DOI treated with placebo and standard therapy.
2. **Secondary Endpoints:**
 - a) Incidence of flares: flare rates during 40 weeks randomization period in patients with IIM treated with belimumab and patients treated with placebo and at week 64 in each group.
 - b) Time to achieve initial improvement defined as the time to reaching DOI.
 - c) Duration of improvement; quantified as the time from achieving improvement to the time of worsening or a disease flare. (Time from 1st DOI to 1st DOW or disease flare event). This will be based on the subset of subjects who achieve improvement.
 - d) Percent change in muscle enzyme levels (CPK and myoglobin) from baseline to week 40 and 64 in each respective group
 1. $<20\%$ reduction: no response
 2. 20-70% reduction: partial response
 3. $>70\%$ reduction: complete response
 - e) Percent change in manual muscle assessment (MMT-8) from baseline to week 40 and week 64 in each respective group.

- 1. <20% reduction: no response
- 2. 20-70% reduction: partial response
- 3. >70% reduction: complete response
- f) Percent change in prednisone dose from baseline to week 40 and week 64 in each respective group
- g) Proportion of subjects, among those on steroids at baseline, able to reduce the prednisone dose to ≤ 5 mg daily at week 40 and week 64 in each respective group.
- h) Flare rate in placebo group during the 40 week randomized treatment phase as compared to that group in the 20 week open label phase.
- i) Serious adverse event and adverse event rates
- j) Changes in B cell populations from baseline to week 40 and week 64
- k) Changes in autoantibody titers from baseline to week 40 and week 64
- l) Changes in immunoglobulin concentrations from baseline to week 40 and week 64

Inclusion Criteria:

Subjects enrolled in the study must meet the following inclusion criteria:

- 1) Adults ≥ 18 years of age
- 2) Have a diagnosis of:
 - a. definite or probable dermatomyositis (DM) by modified Bohan & Peter criteria or

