Adverse Event (AE): Any untoward medical occurrence in a patient or clinical investigation subject, temporally associated with the use of a medicinal product, whether or not considered related to the medicinal product. Note: An AE can therefore be any unfavorable and unintended sign (including an abnormal laboratory finding), symptom, or disease (new or exacerbated)

temporally associated with the use of a medicinal product. For marketed medicinal products, this also includes failure to produce expected benefits (i.e., lack of efficacy), abuse or misuse.

Events meeting the definition of an AE include:

- Exacerbation of a chronic or intermittent pre-existing condition including either an increase in frequency and/or intensity of the condition
- New conditions detected or diagnosed after study treatment administration even though it may have been present prior to the start of the study
- Signs, symptoms, or the clinical sequelae of a suspected interaction
- Signs, symptoms, or the clinical sequelae of a suspected overdose of either study treatment or a concomitant medication (overdose per se will not be reported as an AE/SAE) unless this is an intentional overdose taken with possible suicidal/self-harming intent. This should be reported regardless of sequelae.

Events that do not meet the definition of an AE include:

- Medical or surgical procedure (e.g., endoscopy, appendectomy); the condition that leads to the procedure is an AE
- Situations where an untoward medical occurrence did not occur (social and/or convenience admission to a hospital)
- Anticipated day-to-day fluctuations of pre-existing disease(s) or condition(s) present or detected at the start of the study that do not worsen
- The disease/disorder being studied, or expected progression, signs, or symptoms of the disease/disorder being studied, unless more severe than expected for the subject's condition

Common adverse events seen in the belimumab lupus trials include; nausea, diarrhea, pyrexia, nasopharyngitis, bronchitis, pain in the extremities, depression, migraine and pharyngitis

Serious Adverse Event (SAE): A serious adverse event is any untoward medical occurrence that, at any dose:

- a. Results in death

NOTE: Any death that occurs during study participation must be reported within 24 hours to the lead site and study sponsor. The investigator must identify etiology, relationship to study drug and an SAE case report form must be completed.

- b. Is life-threatening.

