- c. Testing for latent TB is a standard of care for patients on immunosuppressive therapy and results will be obtained **from their medical record**. If no TB history is found for these patients, a Quantiferon Gold or PPD test will be performed prior to Day 0 as part of **standard of care**.
- d. Hepatitis status will be obtained from patients' **medical records**. If unavailable, testing will be done as part of **standard of care** during the screening period.
- Vital signs will be assessed prior to infusion and after the infusion at every visit.
- Adverse events assessed at every visit. Criteria for grading toxicity will be based on NCI's Common Terminology Criteria for Adverse Events version 4.03. (Adverse Events/Serious Adverse Events (CTCAE Version 4.03)
- A Physical Exam will be performed by the Investigator at Screening, Day 0, Week 8, 16, 24, 32, 40, 52, & 64.
- Urine Pregnancy testing for WOCBP will be conducted at each study visit and 16 weeks after last dose. Urine pregnancy tests must be completed < 7 days prior to the first dose and prior to each IP administration, but not more than once a month. In the event that the urine pregnancy test is indeterminate, a serum pregnancy test will be done.
- Laboratory tests: CBC, Comprehensive metabolic, GGT, ESR, CRP, CPK, myoglobin and urinalysis will be collected at every study visit and follow up week 64.
- An immunoglobulin panel will be collected and assessed at: Screening, Week 40, & 64. Under special circumstances monthly IgG monitoring may be required (see Section: Study Design, part f) and will be performed as part of standard of care.
- Flow Cytometry and RNA-seq are collected at: Day 0, Week 8, 40, Week 48, & Week 60 or 64.
- Cytokine levels (and optional research Northwell only) will be measured at: Day 0, Week 40, & Week 60 or Week 64.
- Patients should be clinically assessed for suicidal ideation and/or behaviour at each study visit using the Columbia Suicide Severity Scale (C-SSRS)
- The Investigator will complete a Physician Global Assessment (PGA, a VAS scale of 10cm), Manual Muscle Test-8 (MMT-8), & Myositis Disease Activity Assessment Tool (MDAAT) at Screening, Day 0, Week 8, 16, 24, 32, 40, 52, & 64
- The Investigator will complete a Muscle Damage Index (MDI) assessment at Screening, Week 40 and Week 64
- Health Assessment Questionnaire (HAQ) and Patient Global Assessment (PGA, a VAS scale of 10cm) will be completed by subjects at Screening, Day 0, Week 8, 16, 24, 32, 40, 52, & 64

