The Biostatistics Randomization Management System (BRMS) is a secure, HIPAA-compliant, web-based application that allows investigators to randomize subjects into randomized clinical trials (RCTs) using their personal computer. The BRMS allows for multi-center, stratified, and single/double blinded RCTs, using permuted blocks. Randomization notifications are automatically sent to the PI and other authorized personnel. Using BRMS is a good way to maintain compliance in RCTs.

Statistical Considerations

SPECIFIC STATISTICAL AIMS

The primary objective of the study is to compare subjects in the Belimumab group and subjects in the placebo group with respect to response (improvement) at week 40.

The specific aims of the study are to compare the two treatment arms (Belimumab vs. Placebo [P vs. B]), during the 40-week randomized phase of the study, with respect to the following:

1. Response at week 40.
2. Flare rates during the 40-week treatment period.
3. Time-to-achieve (initial) improvement during the 40-week randomized phase of the study
4. Duration of improvement during the 40-week randomized phase of the study, among those who achieved improvement (this is essentially a time-to-flare/relapse analysis from the time that you achieved improvement)
5. Change in muscle enzyme levels (CPK, myoglobin) from baseline to week 40
6. Change in MMT-8 from baseline to week 40
7. Change in prednisone dose from baseline to week 40

8. Proportion of subjects able to reduce prednisone dose to ≤ 5 mg at week 40
9. Change in B cell populations, immunoglobulin levels and BLys levels from baseline to week 40.
10. Change in autoantibody titers from baseline to week 40.
11. Rates of SAEs and AEs experienced

STATISTICAL METHODS

All subjects will be analyzed according to the intention-to-treat [ITT] principle. A subject will be considered evaluable and will be included in the intention-to-treat analysis if he/she received at least the first five of the planned infusions during the randomized phase of the study. Subjects who do not get the first five infusions will be considered ‘drop-outs’. It should be noted that the study protocol calls for patients remaining on their treatment assignment. However, adjustments in dosages of medications used in their ‘standard care’ are permitted during the first 8 weeks. Analyses that take into account the actual treatment received (e.g. accounting for compliance, etc.) will be carried out as a secondary analysis (per protocol [PP] analysis).

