treatment and time (baseline vs. week 40; or all available data at each study visit) or other factors of interest will be examined (e.g. Treatment X Disease Type; Treatment X Disease Severity). The treatment-by-time interaction term, will demonstrate whether the trajectories (or patterns of change) in the outcomes of interest are different between treatment groups. Data transformations may be used, in order to meet the necessary assumptions for the mixed models analyses. If transformations do not achieve the assumptions needed, a rank transformation or an appropriate non-parametric method will be considered.

If the analysis using a mixed model approach is not feasible due to the pattern of the data, then, a simplified analysis comparing the two treatment arms with respect to percent change (reductions) in muscle enzymes, MMT-8 and prednisone dose will be carried out using either a t-test or the Mann-Whitney test, as appropriate. A chi-square test or Fisher's exact test, as appropriate, may also be used if the continuous measures are grouped according to pre-specified categories (e.g. reduction in CPK will be categorized as No Response, Partial Response or Complete Response according to whether the percent reduction was <20% vs. 20%-70% vs. >70%, respectively).

6. For specific aim 8, the proportion of subjects who were able to reduce their daily prednisone dose to ≤ 5 mg at week 40, will be compared using either a chi-square test or Fisher's exact test, as appropriate.
7. For specific aim 11, either a chi-square test or Fisher's exact test, as appropriate, will be conducted to compare the proportion of subjects who experienced any SAEs or AEs during the randomized phase of the study. For this analysis, each subject will be categorized at the end of 40 weeks as having had any SAEs/AEs or not having any SAEs/AEs.

Multivariable analyses (logistic, cox) will be conducted for the above outcomes, if feasible. However, this may be limited by the sample size.

SAFETY DATA

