There will be no formal interim analyses or formal statistical stopping rules. However, statistical summaries of adverse event rates using 95% exact confidence intervals will be provided to the data safety monitoring board as need. During regular bi-annual meetings the data safety monitoring board will evaluate the overall rate of adverse events and unanticipated problems. Upon review the group will determine whether there are any changes needed to the anticipated benefit-to-risk assessment and if the study should continue. The results of these regular meetings will be recorded and disseminated to the other participating clinical sites. Safety data will be collected in the form of adverse events (AEs), serious AEs (SAEs) and laboratory parameters (e.g., hematology, chemistry, etc.). AEs will be recorded with the date of onset, severity, relationship to study drug, and disposition. AEs will be translated into a standard classification system such as COSTART or MedDRA. AE data will be summarized according to incidence rates, by treatment arm and by whether or not the AE was treatment related. AEs will be summarized using descriptive statistics and tabulated according to treatment group for each strata. The AE report will be descriptive, rather than inferential.

SAMPLE SIZE CONSIDERATIONS

We plan to enroll 30 evaluable patients with 15 in each of two treatment arms [B vs. P].

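### Item 7 puts serious and other adverse events into one yes/no category and names no population, so the SAE rate has no explicit between-arm comparison and early stoppers can be left out

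*Combined protocol and SAP*

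**What the plan says.** Two rates are promised. Secondary endpoint i is "Serious adverse event and adverse event rates", and aim 11 under Specific Statistical Aims is "Rates of SAEs and AEs experienced", listed among the comparisons of the two arms.

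The only method for aim 11 is item 7 of the Statistical Methods: a chi-square or Fisher's exact test on a proportion, for which "each subject will be categorized at the end of 40 weeks as having had any SAEs/AEs or not having any SAEs/AEs".

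The definitions are in Safety Considerations and Adverse Events. An AE is "Any untoward medical occurrence in a patient or clinical investigation subject, temporally associated with the use of a medicinal product", whether or not it is thought to be related. For SAEs the text reads "A serious adverse event is any untoward medical occurrence that, at any dose", followed by the seriousness criteria.

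Item 7 names no analysis set. The opening of the Statistical Methods covers all subjects and counts a subject as evaluable if "he/she received at least the first five of the planned infusions during the randomized phase of the study". Anyone with fewer infusions is a drop-out. No safety population is defined anywhere.

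The Safety Data section summarizes AE incidence by arm, by relatedness and within strata. It mentions SAEs only as data collected and ends: "The AE report will be descriptive, rather than inferential".

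**The concern.** An SAE is an untoward occurrence that also meets a seriousness criterion, so having any SAE or AE is the same as having any AE. A subject with a mild cold and a subject with a life-threatening infection get the same code. Under Study Procedures & Assessments the plan has "Adverse events assessed at every visit", so over 40 weeks most subjects may have at least one AE. A difference in SAEs would then barely move the comparison.

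The population adds a second weakness. The fifth infusion is at week 12. A subject whose treatment ends before then because of an adverse event falls outside the evaluable set, and that is a subject a safety comparison most needs to count.

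At stake is the usefulness of one secondary safety comparison. No efficacy conclusion depends on it.

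**Working it through.** **Inputs.** From the documents: 15 per arm, and two-sided alpha of 0.05 (set for the primary endpoint and borrowed here as a nominal level). The documents give no AE or SAE rates, so every rate below is an assumption.

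**The plan's own figure.** There is none for safety. The 15 per arm comes from the primary endpoint (5% v 50%, 80% power) and reproduces without continuity correction:

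n = [1.96·√(2·0.275·0.725) + 0.842·√(0.05·0.95 + 0.50·0.50)]² / 0.45² = (1.238 + 0.459)² / 0.2025 = 14.2, so 15.

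**Step 1: the ceiling.** Suppose all 15 belimumab subjects have an AE, the most extreme excess possible. When every event-free subject is in one arm, the two-sided Fisher p is 2·C(15,k)/C(30,k), where k is the number of placebo subjects without an AE.

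- 15/15 v 10/15: 2·3003/142506 = 0.042.
- 15/15 v 11/15: 2·1365/27405 = 0.0996.

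From 11 placebo subjects upward, no belimumab excess reaches Fisher p≤0.05. For the uncorrected chi-square the limit is 12: 15/15 v 11/15 gives p=0.032, and 15/15 v 12/15 gives z = 0.20/√(0.9·0.1·2/15) = 1.83, p=0.068.

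**Step 2: how likely the ceiling is.** P(X≥11) for X ~ Binomial(15, p), where p is an assumed placebo any-AE rate:

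| p | 50% | 70% | 80% | 90% |
|---|---|---|---|---|
| P(X≥11) | 6% | 52% | 84% | 99% |

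**Step 3: what merging costs.** Assume SAEs occur independently of other AEs. With background AE rate b and SAE rate s, the any-AE rate is 1 − (1−b)(1−s). For b=80% and SAEs of 5% v 35%, this is 81% v 87%. Power comes from exact enumeration of the 16×16 outcomes (excess on belimumab, two-sided p≤0.05) and is shown as Fisher (chi-square):

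| SAE rates, placebo v belimumab | SAE tested directly | any AE, b=50% | any AE, b=80% | any AE, b=90% |
|---|---|---|---|---|
| 5% v 35% | 40% (58%) | 6% (13%) | 2% (6%) | 0.4% (2%) |
| 5% v 20% | 8% (19%) | 2% (6%) | 1% (4%) | 0.3% (1%) |

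Merging hides a large SAE excess. A modest one is missed either way, so an estimate with an interval is more useful than a further test.

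**Step 4: an illustration with invented counts.** SAEs of 5/15 v 1/15 give +27 points (exact 95% CI −4 to 55; Fisher p=0.17). If any AE is 14/15 v 12/15, item 7 returns p=0.60 (+13 points, −14 to 43) however the SAEs fall. If 2 of the 5 belimumab subjects with an SAE stopped before the fifth infusion, the evaluable set shows 3/13 v 1/15, which is +16 points (−12 to 48). The intervals are exact unconditional: two one-sided 2.5% score tests inverted on a grid of 0.01.

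**Step 5: can an adverse event end treatment before week 12?** Yes. Appendix C requires study treatment to be discontinued at once after a liver stopping event. Study Drug Administration requires administration to stop after a serious reaction and notes that infusion reactions were more frequent on the first two infusion days. That instruction could mean stopping only the infusion in progress, so Appendix C is the firmer support.

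**The case against.** **The slash may be shorthand for two analyses.** Aim 11 and endpoint i name both rates, and naming SAEs would be redundant if one flag were meant. This is a fair reading and may be the intended one. But item 7 describes one category per subject, whereas item 5 says explicitly that its outcomes are analyzed separately. The wording still has to be settled.

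**SAEs are not lost.** A reader might infer that the plan conceals serious events. It does not. Each SAE goes on a case report form, and the by-arm AE incidence summaries would include SAEs among all AEs. What is missing is an explicit SAE comparison.

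**The clash with the Safety Data section.** A reader might infer that item 7's test contradicts the descriptive AE report. The closing sentence of that section may govern only the tabulated report and leave item 7 as the one formal comparison. The text does not fix its scope, so this is an ambiguity and not an established conflict.

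**The five-infusion rule is framed for the intention-to-treat analysis.** AEs are collected from the start of treatment, and the Safety Data section does not repeat the rule. That is true, but item 7 sits under the rule with no set of its own, so the rule applies by default. The 3/13 example also assumes that drop-outs are not replaced, whereas the plan speaks of 30 evaluable patients.

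**The practical gain is small.** With 15 per arm the SAE interval in the illustration is inconclusive too. This stands, and it limits the severity.

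**Conclusion.** The point holds as a minor one. Read literally, item 7 compares any AE, and the SAE rate named as an endpoint gets no explicit between-arm comparison. The default evaluable set can also leave out subjects who stop before week 12 because of an adverse event.

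The ceiling at 11 of 15 (Fisher) is arithmetic. Whether the trial would reach it depends on AE rates that the documents do not give, and the chance runs from 6% to 99% over assumed rates of 50% to 90%. The power comparison also assumes that SAEs are independent of other AEs.

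A reader might go on to infer that the planned test is wrong and must be removed. The documents do not support that: the aims are stated as comparisons of the two arms, and a nominal test of each rate is compatible with them. The primary analysis, alpha and sample size are unaffected.

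**What to change.** Replace item 7 with wording such as:

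> For specific aim 11, the proportion of subjects with at least one SAE, and separately with at least one AE, during the randomized phase will be given by arm among all subjects who received at least one infusion, analyzed by treatment received, with the risk difference and exact 95% CI.

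Add one sentence saying whether the chi-square or Fisher test is kept as a nominal comparison for each rate or dropped. Either is acceptable, but the plan should say which, because the Safety Data section calls the AE report descriptive.

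The cost is two table lines from data already collected. The downsides are wide intervals and a safety denominator that may differ from the 30 evaluable subjects, which a footnote can explain.

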Appendix A. Study Schedule

	SCREENING PHASE	RANDOMIZED TREATMENT PHASE												OPEN LABEL TREATMENT PHASE							Post Treatment Follow Up				
		Screening	Day 0	Week 2*	Week 4*	Week 8	Week 12*	Week 16	Week 20*	Week 24	Week 28*	Week 32	Week 36*	Week 40	Week 40	Week 44*	Week 48*	Week 52	Week 56*	Week 60*	Week 64	Week 72	Week 76	Week 84	
Clinical/Physical																									
Informed Consent	X																								
Inclusion/Exclusion Criteria	X																								
Physical Exam and History	X	X			X		X		X		X		X	X				X			X				
Vital Signs	X	X	X	X	X	X	X	X	X	X	X	X	X	X	X	X	X	X	X	X	X	X	X		
Assess AE	X	X	X	X	X	X	X	X	X	X	X	X	X	X	X	X	X	X	X	X	X	X	X		
MMT	X	X			X		X		X		X		X	X				X			X			X	
MDAAT	X	X			X		X		X		X		X	X				X			X			X	
Physician Global Assessment	X	X			X		X		X		X		X	X				X			X			X	
MDI	X																	X						X	
C-SSRS	X	X	X	X	X	X	X	X	X	X	X	X	X	X	X	X	X	X	X	X	X	X	X	X	
HAQ (completed by subject)	X	X			X		X		X		X		X	X				X			X			X	
Patient Global Assessment (completed by subject)	X	X			X		X		X		X		X	X				X			X			X	
Post Study Follow Up Phone Call w/Subject																						X			X
Study Agent Administration		X	X	X	X	X	X	X	X	X	X	X	X	X	X	X	X	X	X	X	X	X	X		
Laboratory																									
CBC w/differential	X	X	X	X	X	X	X	X	X	X	X	X	X	X	X	X	X	X	X	X	X	X	X		
Comprehensive Metabolic Panel (AST, ALT, ALP incl.)	X	X	X	X	X	X	X	X	X	X	X	X	X	X	X	X	X	X	X	X	X	X	X		
GGT Liver Enzyme	X	X	X	X	X	X	X	X	X	X	X	X	X	X	X	X	X	X	X	X	X	X	X		
ESR	X			X		X		X		X		X		X		X		X		X		X		X	
CRP	X	X		X		X		X		X		X		X		X		X		X		X		X	
CPK total	X	X		X		X		X		X		X		X		X		X		X		X		X	
Serum Myoglobin	X	X		X		X		X		X		X		X		X		X		X		X		X	
Urinalysis w/Microscopy	X	X		X		X		X		X		X		X		X		X		X		X		X	
Immunoglobulins (IgG, IgA, IgM)	X																	X						X	
Pregnancy test (WOCBP) [§]	X	X	X	X	X	X	X	X	X	X	X	X	X	X	X	X	X	X	X	X	X	X	X	X	
Flow Cytometry		X‡			X‡											X‡			X‡			X‡	X‡		
RNA-Seq	X‡			X‡												X‡			X‡			X‡	X‡		
Cytokine Levels		X□														X□						X□	X□		
Optional Research Sampling (Northwell Only)			X£			X£										X£			X£			X£	X£		

* Note: Patients will be monitored, assessed and have routine blood tests performed according to standard of care at each infusion visit

§ Note: Pregnancy testing will occur at each outlined study visit and at 16 weeks after the last treatment dose

† Note: Blood samples should be collected at the following time points: Day 0, Week 8, 40, Week 48, Week 60 or 64

‡ Note: Blood samples should be collected at the following time points: Day 0, 40, Week 60 or 64

£ Note: Optional Blood samples should be collected at the following time points: Day 0, Week 8, Week 40, Week 48, Week 60 or Week 64

